10.3.2 Presentation of Pharmacokinetic Data

Presentation of Pharmacokinetic Plasma Drug Concentration Data

The following rules will be applied if there are values that are BLQ or if there are missing values (eg, no result [NR]) in a plasma concentration data series to be summarized.

- For the calculation of summary statistics, BLQ values will be set to zero.
- If an embedded BLQ value is considered anomalous within the concentration-time profile, this value will be excluded from the summary statistics.
- Where there is NR, these will be set to missing.
- If there are less than three values in the data series, only the minimum, maximum and number of subjects will be presented. The other summary statistics will be denoted as not calculated (NC). BLQ is considered a value.
- If all the values are BLQ, then the arithmetic mean, arithmetic CV%, arithmetic standard deviation, median, minimum and maximum will be presented as zero, and the geometric mean and geometric CV% will be denoted as NC.
- If the value of the arithmetic mean or median is below the lower limit of quantification, these values will be presented as zero and the geometric mean and geometric CV% will be denoted as NC.

Presentation of Pharmacokinetic Parameters

For the calculation of summary statistics of PK parameters, all NR and NC values in a data series will be set to missing.

The AUC values will be set to NC if they did not meet minimum data requirements for calculation.

10.3.3 Pharmacokinetic Statistical Methodology

A statistical analysis will be conducted to investigate the drug-drug interaction on the PK of LOXO-292 for AUC_{0-t} , $AUC_{0-\infty}$ and C_{max} . The comparisons of interest are:

- LOXO-292 (fasted) co-administered with ranitidine vs LOXO-292 (fasted)
- LOXO-292 (fed) co-administered with omeprazole vs LOXO-292 (fasted)

The primary analysis planned for this study is an Analysis of Variance (ANOVA) model that includes treatment as a fixed-effect and subject as a random-effect. CCI

[REDACTED]

[REDACTED]

CCI

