Twenty healthy, adult, male and female subjects (women of nonchildbearing potential only) are considered sufficient to assess the effect of multiple doses of an H2 antagonist (under fasted conditions) or a PPI (given with a low-fat meal) on the PK of LOXO-292.

Every attempt will be made to enroll at least 3 subjects of each sex in the study.

Subjects who withdraw or drop out of the study may be replaced if deemed necessary by the Sponsor.

Diagnosis and main criteria for inclusion:

Male subjects and female subjects of nonchildbearing potential, between 18 and 55 years of age, inclusive, at Screening, and within body mass index (BMI) range 18.5 to 32.0 kg/m², inclusive. Subjects will be in good general health, based on medical history, PE findings, vital signs, ECG, and clinical laboratory tests at Screening and Check-in (Day -1), as determined by the Investigator (or designee).

Investigational products, dose, and mode of administration:

LOXO-292 will be supplied by Loxo Oncology as 80 mg capsules for oral administration. Ranitidine will be supplied by Covance as 150 mg tablets for oral administration. Omeprazole will be supplied by Covance as 40 mg capsules for oral administration

Period 1: Subjects will be administered 160 mg LOXO-292 (2 x 80 mg capsules) on Day 1 administered under fasted conditions.

Period 2: Subjects will be administered 150 mg of rantidine twice daily from Day 8 of through Day 18, inclusive, administered with 160 mg LOXO-292 on Day 12 under fasted conditions.

Period 3: Subjects will be administered 40 mg of omeprazole once daily from Day 19 through Day 29, inclusive, administered with 160 mg LOXO-292 on Day 23 with a low-fat meal.

Duration of subject participation in the study:

Planned Enrollment/Screening Duration: up to 28 days (Day -29 to Day -2).

Length of Confinement: a total of 31 days (30 nights), from the time of Check-in (Day -1) through the 168-hour PK blood draw and end of study assessments (Day 30).

Follow-up Phone Call: 7 days (\pm 2 days) after EOT or ET.

Planned Study Conduct Duration: approximately 60 days

Criteria for evaluation:

Pharmacokinetics:

Serial PK blood samples for the analysis of plasma LOXO-292 concentrations will be collected from predose through 168 hours postdose.

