The following PK parameters will be calculated whenever possible, based on the plasma concentrations of LOXO-292 (as appropriate): area under the concentration-time curve from Hour 0 to the last measurable concentration (AUC_{0-t}), area under the concentration time curve extrapolated to infinity ($AUC_{0-\infty}$), extrapolation for area under the concentration time curve (% AUC_{extrap}), maximum plasma concentration (C_{max}), time to maximum observed concentration (t_{max}), elimination rate constant (λZ), apparent systemic clearance (CL/F), and apparent terminal elimination half-life ($t_{1/2}$).

An analysis of variance (ANOVA) will be performed on the natural log (ln)transformed AUC_{0-t} , $AUC_{0-\infty}$, and C_{max} , using the appropriate statistical procedure.

Safety:

Safety will be monitored through 12-lead ECGs, PEs, concomitant medications, vital sign measurements, clinical laboratory tests, and AEs.

CCI

Statistical methods:

Pharmacokinetics:

The primary analysis planned for this study is an analysis of variance (ANOVA) model that includes treatment as a fixed-effect and subject as a random-effect. CCI [REDACTED]

Safety:

All safety assessments, including AEs and SAEs, vital signs measurements, clinical laboratory results, PE results, concomitant medications, and ECG interpretations, will be tabulated and summarized where possible, using descriptive methodology, as needed, by timepoint. Unless otherwise specified, baseline value is defined as the last nonmissing measurement before administration of LOXO-292 in each period. No formal statistical analyses are planned for the safety data.

More details on the analyses will be included in the Statistical Analysis Plan (SAP).

TABLE OF CONTENTS

TITLE PAGE	1
STUDY IDENTIFICATION	2
PRINCIPAL INVESTIGATOR AND SPONSOR – SIGNATORIES	3
SYNOPSIS	4
TABLE OF CONTENTS	8
LIST OF TABLES AND FIGURES	11
LIST OF ABBREVIATIONS	12
1. INTRODUCTION	15
1.1. Background	15
1.2. Summary of Nonclinical Studies	15
1.3. Summary of Clinical Studies	16
1.4. Study Rationale	18
1.5. Benefit-risk Assessment	18
2. OBJECTIVES AND ENDPOINTS	19
2.1. Objectives	19
2.2. Endpoints	19
3. INVESTIGATIONAL PLAN	20
3.1. Overall Study Design and Plan	20
3.2. Discussion of Study Design	21
3.3. Selection of Doses in the Study	22
4. SELECTION OF STUDY POPULATION	22
4.1. Screening Procedures	22
4.2. Check-in Procedures (Day -1)	23
4.3. Inclusion Criteria	24
4.4. Exclusion Criteria	25
4.5. Subject Number and Identification	29

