8.3.1. Descriptive Analysis

Plasma concentrations and PK parameters will be summarized with descriptive statistics (number, arithmetic mean, standard deviation, coefficient of variation [CV%], geometric mean, geometric CV%, median, minimum, and maximum).

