8.3.2. Analysis of Variance (ANOVA)

The primary analysis planned for this study is an ANOVA model that includes treatment as a fixed-effect and subject as a random-effect. CCI

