7 TREATMENTS

The following is a list of the study treatment sequence abbreviations and ordering that will be used in the baseline TFLs.

Study Treatment labels	Treatment Order on TFLs
Treatment sequence label	
160 mg LOXO-292/ 160 mg LOXO-292 + 150 mg ranitidine BID/ 160 mg LOXO-292 + 40 mg omeprazole QD	
Treatment labels	
160 mg LOXO-292	1
150 mg ranitidine BID	2
160 mg LOXO-292 + 150 mg ranitidine BID	3
40 mg omeprazole QD	4
160 mg LOXO-292 + 40 mg omeprazole QD	5
PK outputs	
160 mg LOXO-292 (fasted)	1
160 mg LOXO-292 (fasted) + 150 mg ranitidine BID	2
160 mg LOXO-292 (fed) + 40 mg omeprazole QD	3

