10 STATISTICAL METHODOLOGY

10.1 General

Data listings will be provided for the All Subjects Population. Summary statistics and statistical analyses will be performed for subjects included in the relevant analysis populations (Safety/PK).

For continuous data, summary statistics will include the arithmetic mean, (arithmetic coefficient of variation (CV%) and standard error of the mean (SEM) for PK summaries), arithmetic standard deviation, median, minimum, maximum, and number. For log-normal data (eg, the PK parameters: areas under the concentration-time curve [AUCs] and maximum observed concentration [C_{max}]), the geometric mean and geometric coefficient of variation (CV%) will also be presented. For categorical data, frequency counts and percentages will be presented. Data listings will be provided for all subjects up to the point of withdrawal, with any subjects excluded from the relevant population highlighted. For the calculation of summary statistics and statistical analysis, unrounded data will be used.

Missing values will not be imputed.

Data analysis will be performed using SAS® Version 9.4.

Analysis Data Model (ADaM) datasets will be prepared using Clinical Data Interchange Standards Consortium (CDISC) ADaM Version 2.1, and CDISC ADaM Implementation Guide Version 1.1. Pinnacle 21 Community Validator Version 2.2.0 will be utilized to ensure compliance with CDISC standards.

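### Does the primary ANOVA make each drug-interaction comparison use error variance from a period that it does not compare?

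*SAP*

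**What the plan says.** SAP 10.3.3 analyses AUC0-t, AUC0-∞ and Cmax and lists two comparisons. One is fasted LOXO-292 with ranitidine against fasted LOXO-292 alone. The other is fed LOXO-292 with omeprazole against the same fasted reference. It names the model as an "Analysis of Variance (ANOVA) model that includes treatment as a fixed-effect and subject as a random-effect". Protocol 8.3.2 agrees: "The primary analysis planned for this study is an ANOVA model that includes treatment as a fixed-effect and subject as a random-effect". The Protocol Synopsis adds the scale: "An analysis of variance (ANOVA) will be performed on the natural log (ln)transformed" AUC and Cmax values.

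In SAP 10.3.3, in Protocol 8.3.2 and under statistical methods in the Synopsis, redacted text follows the model sentence directly. SAP 12 reports no change from the protocol's analyses. SAP 7 lists three PK conditions: fasted, fasted with ranitidine, and "160 mg LOXO-292 (fed) + 40 mg omeprazole QD". The planned size is given in the Synopsis: "Twenty healthy, adult, male and female subjects". Its justification (Protocol 8.1, SAP 8) is redacted.

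**The concern.** Anyone who has fitted this kind of model will picture one data set with three records per subject and one residual variance. Both contrasts then receive the same standard error, although each compares only two of the three periods. The conditions are unlike: Period 3 changes both acid suppression and meal state, and Protocol 1.4 says that solubility depends on pH. If omeprazole with food made exposure more variable within subjects, a pooled error would make the omeprazole interval too narrow and the ranitidine interval too wide. A noisier Period 2 would reverse the roles, and a noisier Period 1 would make both too narrow.

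The stake is the width and coverage of the two primary intervals. With complete data the point estimates are the same either way. The planned geometric CV% (Protocol 8.3.1, SAP 10.1) would not expose the problem, because it mixes between-subject and within-subject variation.

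**Working it through.** **Inputs.** From the documents: 20 subjects (Protocol Synopsis), three periods in a fixed sequence (SAP 6), two contrasts against Period 1 (SAP 10.3.3), log scale (Synopsis). Not visible and therefore assumed: a two-sided 90% interval (95% as an alternative), a base within-subject ln SD of 0.25, and complete data. The plan shows no interval width, power or SD, so there is no figure of its own to reproduce.

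**Step 1: what the visible text fixes.** It fixes treatment as a fixed effect and subject as a random effect. It does not say whether there is one fit or two, whether the residual variance is common, which degrees of freedom apply, or what the interval level is. Such details would normally follow the model sentence, and that is where the redaction begins.

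**Step 2: what a pooled fit would do, if used.** Let v_jk be the variance of the ln difference between periods j and k. Then:

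- expected pooled MSE = (v12 + v13 + v23)/6
- model SE = √(2·MSE/n), with 2(n − 1) = 38 df
- true SE for Period k against Period 1 = √(v1k/n)

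Let the Period 3 SD be r times the others, with independent errors and the common variance set to 1. Then v12 = 2 and v13 = v23 = 1 + r², so MSE = (2 + r²)/3. The ratio of model SE to true SE is √[(2 + r²)/3] for ranitidine and √[2(2 + r²)/(3(1 + r²))] for omeprazole. At r = 2 these are √(6/3) = 1.414 and √(12/15) = 0.894. Coverage below comes from 200,000 simulated trials per case.

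| r | SE ratio, ranitidine | SE ratio, omeprazole | Pooled coverage, ranitidine / omeprazole |
|---|---|---|---|
| 0.8 | 0.938 | 1.036 | 87.7 / 91.2% |
| 1.0 | 1.000 | 1.000 | 89.9 / 90.0% |
| 1.2 | 1.071 | 0.969 | 92.2 / 89.0% |
| 1.5 | 1.190 | 0.934 | 94.6 / 87.5% |
| 2.0 | 1.414 | 0.894 | 97.7 / 85.9% |

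Two-period fits cover 89.8% to 90.2% throughout. The mechanism is therefore real, but its size depends entirely on r, and the documents give no value for r.

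**Step 3: when the pooled fit is valid.** The sufficient condition is that v12, v13 and v23 are equal. This does not require the absence of a subject-by-treatment interaction. With within-subject variance σ² and an independent interaction of equal variance τ² in each condition, every v_jk = 2σ² + 2τ². Then MSE = σ² + τ² and model SE² = 2(σ² + τ²)/n, which equals the true value. Simulation with τ² = 0.04 gives 90.1 / 90.0%. Unequal period variances can also be harmless: 0.1625, 0.1225 and 0.3025, with equal difference variances, give 90.0 / 90.2%. Unlike conditions do not by themselves show that a pooled interval fails.

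**Step 4: the price of separate fits.** The t multipliers at 90% are 1.729 (19 df) and 1.686 (38 df), a ratio of 1.729/1.686 = 1.026. Mean ln half-widths at equal SDs are 0.1349 and 0.1324, a ratio of 1.019. At 95% the mean width rises 2.7%. This is the cost when the pooled interval is also correct.

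**The case for a change.** The strongest case for the concern is that the trade looks lopsided. Separate fits cost about 2% in width when the pooled assumption holds, and protect coverage when it does not. Protocol 1.4 shows how far absorption can move. With omeprazole under fasting, AUC and Cmax were about 69% to 88% lower. With omeprazole and a high-fat meal, AUC was about 2% higher but Cmax about 49% lower. Equal difference variances cannot be taken for granted, and an unstructured covariance would serve a sponsor who prefers one fit.

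The algebra stands, and so does the advantage of two-period fits with complete data. Two things do not follow. First, the figures in Protocol 1.4 are shifts in mean exposure; they do not measure within-subject variance in any condition. Second, the argument needs a pooled three-period fit with one residual variance, and no visible sentence specifies one. Separate fits are also not exact in every case: if 4 of 20 subjects lack Period 3 and its SD is doubled, the two-period omeprazole interval covers about 88.4%. That is better than the pooled 83.7% but below 90%. What remains is a question that anyone holding the unredacted SAP can answer by reading it.

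**Conclusion.** There is no fault here. The visible model sentence is correct and compatible with either way of fitting, the Protocol and SAP agree on it, and the detail that would decide the matter lies in redacted text. No stated rule gives a wrong result.

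If the redacted text did specify a pooled fit, that would be a defensible choice at n = 20. It has 38 rather than 19 degrees of freedom, it is valid when the difference variances are equal, and it is off by 1.0 to 2.3 points of coverage at Period 3 SD ratios of 0.8 or 1.2. The larger departures (97.7% and 85.9%) need a doubled SD, for which the documents give no support. No decision boundary is visible, so no changed conclusion can be claimed.

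These sizes rest on an assumed 90% level, 20 completers and an assumed ln SD of 0.25. The conclusion that the plan contains no error depends on none of them.

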10.4 Safety and Tolerability Assessments

10.4.1 Adverse Events

An event is defined as an AE if the event occurs after signing of the ICF but prior to study drug administration on Day 1 and is assessed as related to study procedures by the Investigator [or designee]. A treatment-emergent AE (TEAE) is defined as an AE that occurs postdose or that is present predose and becomes more severe postdose. The AE severity and relationship are determined by the investigator at the site. The severity grade of each AE will be based on the National Cancer Institute's Common Terminology Criteria for Adverse Events (CTCAE, Version 5.0) 5-point severity scale (Grade 1, 2, 3, 4 and 5). Not all grades are appropriate for all AEs. Therefore, some AEs are listed within the CTCAE with fewer than 5 options for grade selection.

A TEAE occurring during or after Day 1 dosing and up to predose Day 8 will be assigned to treatment 160 mg LOXO-292. A TEAE occurring after Day 8 dosing and up to Day 11 will be assigned to 150 mg ranitidine. A TEAE occurring after Day 12 dosing and up to Day 19 predose will be assigned to 160 mg LOXO-292 + 150 mg ranitidine. A TEAE occurring after Day 19 dosing and predose Day 22 will be assigned to 40 mg omeprazole QD. A TEAE occurring after Day 23 dosing until Follow-up will be assigned to 160 mg LOXO-292 + 40 mg omeprazole QD.

All AEs will be listed. The TEAEs will be summarized by treatment, severity, and relationship to the study drug. The frequency (the number of TEAEs, the number of subjects experiencing a TEAE, and the percentage of subjects experiencing a TEAE) of TEAEs will be summarized by treatment, and by Medical Dictionary for Regulatory Activities system organ class and preferred term. A frequency summary will be presented by day of onset across the multiple-dosing period. The summary and frequency TEAE tables will be presented for all causalities and for those TEAEs considered related to the study drug (those that have a relationship of "Related"). Any severe or serious AEs will be tabulated. For any AEs that change severity ratings for a given treatment, the AE will be included only once under the maximum severity rating in the summaries. If a TEAE decreases in severity grade, the new TEAE record with lesser severity will be counted as the same TEAE event of the previous record with worse severity under the same treatment group. Onset times postdose are calculated from the last dose administered. Discontinuations due to AEs will be listed.

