^e Electrocardiograms will be collected after the subject has rested in the supine position for at least 10 minutes, and will be obtained prior to and as close as possible to the scheduled blood draws at Screening and Day -1, Day 1 (before LOXO-292 dosing), Day 2, Day 8 (before ranitidine dosing), Day 12 (before LOXO-292 dosing), Day 13, Day 19 (before omeprazole dosing), Day 23 (before LOXO-292 dosing), Day 24, and EOT (or ET).

^f Vital signs measurements (oral temperature, respiratory rate, and supine blood pressure and heart rate) will be obtained Screening and Day -1, Day 1 (before LOXO-292 dosing), Day 2, Day 8 (before ranitidine dosing), Day 12 (before LOXO-292 dosing), Day 13, Day 19 (before omeprazole dosing), Day 23 (before LOXO-292 dosing), Day 24, and EOT (or ET). Vital signs measurements should be carried out prior to and as close as possible to having blood drawn. Blood pressure and HR will be measured using the same arm for each reading after the subject has been supine for at least 5 minutes.

^g An HDYF? inquiry performed at Screening (after the ICF is signed), at Check-in (Day -1), at each postdose vital signs assessment, and at an appropriate time for all other days.

^h AEs and SAEs will be collected beginning at informed consent. AEs will be recorded throughout the study (ie, from signing of the ICF until EOS, or until ET if the subject discontinues from the study and does not complete a follow-up phone call), either as subject medical history (if the event is reported as beginning prior to signing of the ICF or if the event occurs prior to study drug administration on Day 1 and is assessed as not related to study procedures by the Investigator [or designee]) or as AEs (if the event occurs after signing of the ICF but prior to study drug administration on Day 1 and is assessed by the Investigator [or designee] as related to study procedures, or if the event occurs after study drug administration on Day 1 through EOT or ET regardless of relationship to study drug). From EOT or ET through EOS, only AEs assessed as related to study drug are to be recorded. All SAEs that develop from the time of ICF signing until EOS (or ET if the subject discontinues from the study and does not complete a follow-up phone call) are to be reported.

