ⁱ LOXO-292 will be administered in the morning of Days 1 and 12, following a fast of 10 hours prior to and 4 hours after the LOXO-292 dose. On Day 23, LOXO-292 will be coadministered with omeprazole within 30 minutes of the start of a low-fat meal which will be entirely consumed within 30 minutes.

^j On Day 12, ranitidine will be administered 2 hours (\pm 10 minutes) after the LOXO-292 dose. On Days 8 - 11 and 13 - 18, the morning dose of ranitidine will be administered (with breakfast) approximately 2 hours (\pm 1 hour) after the planned or actual time of the Day 12 LOXO-292 dose and the evening dose of ranitidine will be administered (with a light meal/snack) approximately 10 hours (\pm 1 hour) prior to the planned or actual time of the Day 12 LOXO-292 dose.

^k On Day 23, omeprazole and a single oral dose of 160 mg of LOXO-292 will be coadministered within 30 minutes of the start of a low-fat meal, which will be entirely consumed within 30 minutes. On Days 19-22 and 24-29, omeprazole will be administered following a fast of 2 hours prior to and 1 hour after the omeprazole dose (Note: omeprazole will be administered at approximately the actual time of the Day 12 LOXO-292 dosing).

^l Primary PK blood samples will be collected prior to dosing (within 30 minutes) and 0.25, 0.5, 0.75, 1, 1.5, 2, 2.5, 3, 4, 6, 8, 12, 24, 48, 72, 96, 120, 144, and 168 hours after LOXO-292 administration on Days 1, 12, and 23 for Periods 1, 2, and 3, respectively. The allowed sampling window for PK blood samples will be the following: within 15 minutes prior to dosing for the predose sample timepoint; \pm 5 minutes for sampling timepoints within the first 12 hours; \pm 30 minutes for sampling timepoints > 12 hours < 36 hours; and \pm 60 minutes for the sampling timepoints ranging from 48 to 168 hours.

^m Clinical chemistry panel including CK (fasted at least 8 hours), coagulation parameters, complete blood count, and urinalysis will be performed at Screening, Check-in (Day -1), and Days 2, 7, 11 (before ranitidine dosing), 13, 18 (before ranitidine dosing), 22 (before omeprazole dosing), and 24; and at EOT (Day 30) or ET.

ⁿ Hemoglobin A1c test performed at Screening only.

^o Alcohol breath test and drugs of abuse urine test, including cotinine. Results from the alcohol and drug tests will be used to determine subject eligibility per the inclusion/exclusion criteria.

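### The adverse-event windows in SAP 10.4.1 do not join at Day 22/23 or Day 11/12, so onsets in those gaps have no treatment group

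*SAP*

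**What the plan says.** SAP 10.4.1 sets five onset windows. LOXO-292 alone runs from Day 1 dosing until before the Day 8 dose. The other four read:

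- Ranitidine alone: "A TEAE occurring after Day 8 dosing and up to Day 11 will be assigned to 150 mg ranitidine".
- LOXO-292 with ranitidine: "A TEAE occurring after Day 12 dosing and up to Day 19 predose will be assigned to 160 mg LOXO-292 + 150 mg ranitidine".
- Omeprazole alone: "A TEAE occurring after Day 19 dosing and predose Day 22 will be assigned to 40 mg omeprazole QD".
- LOXO-292 with omeprazole: "A TEAE occurring after Day 23 dosing until Follow-up will be assigned to 160 mg LOXO-292 + 40 mg omeprazole QD".

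The tables depend on these windows: "The TEAEs will be summarized by treatment, severity, and relationship to the study drug". SAP 7 gives each antacid-alone phase its own treatment label. The same SAP section counts as a TEAE any adverse event that occurs after dosing, or that was present before dosing and then worsens.

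**The concern.** At Day 8 and Day 19 one window closes before that day's dose and the next opens after it, so nothing falls between them. At the other two boundaries the closing and opening days differ. Omeprazole alone closes before the Day 22 dose although LOXO-292 is not given until Day 23. Ranitidine alone closes at Day 11, with no dose or clock time attached, although LOXO-292 is not given until Day 12.

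Subjects are on an antacid during both gaps, so an event that starts there is a TEAE but has no treatment. SAP 10.4.1 counts events and subjects by treatment and resolves changes in severity within a treatment, so those rules cannot be applied to it as written. The programmer would have to leave the event out of the by-treatment tables or choose a group with the data in view.

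Scheduled assessments fall in the gaps. The ECG schedule in Protocol Appendix 4 includes "Day 8 (before ranitidine dosing), Day 12 (before LOXO-292 dosing), Day 13, Day 19 (before omeprazole dosing), Day 23 (before LOXO-292 dosing"), and vital signs follow the same days. Protocol 7.2.1 records adverse events noted at these checks. An event first seen at, and dated to, the pre-dose check on Day 12 or Day 23 would be unassigned. The readings themselves are safe, because SAP 10.1.1 makes them the period baselines.

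**Working it through.** **Inputs**

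- Window limits: SAP 10.4.1.
- Dosing days: ranitidine Days 8 to 18, omeprazole Days 19 to 29 (SAP 6); LOXO-292 Days 1, 12 and 23 (SAP 10.1.1).
- Lead-in: four consecutive days of each antacid before LOXO-292 (Protocol 3.3).
- Omeprazole is given at about the clock time of the Day 12 LOXO-292 dose; the morning ranitidine dose is about 2 h (±1 h) after that time (SAP 6).
- T is the clock hour of the LOXO-292 dose. Protocol Appendix 4 says only that "LOXO-292 will be administered in the morning of Days 1 and 12". Assumption: T lies between 07:00 and 10:00. Day 12 dosing is taken to mean the LOXO-292 dose, and Day 23 dosing is taken to be at about the same clock time as on Day 22.

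**Check of the plan's own figure.** Ranitidine lead-in: 12 − 8 = 4 days. Omeprazole lead-in: 23 − 19 = 4 days. Both agree with Protocol 3.3.

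**Omeprazole alone**

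- Phase: Day 19 at T to Day 23 at T = 4 × 24 = 96 h.
- Gap: Day 22 at T to Day 23 at T = 24 h.
- Share: 24/96 = 25%. This is the whole interval after the last of the four omeprazole-alone doses. It does not depend on the value of T.

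**Ranitidine alone**

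- Phase: Day 8 at T + 2 h (±1 h) to Day 12 at T. This is 96 − 3 = 93 h to 96 − 1 = 95 h.
- The gap depends on how the Day 11 limit is read:

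| Reading of the Day 11 limit | Gap before Day 12 at T | Share of phase |
|---|---|---|
| All of Day 11 included | 00:00 on Day 12 to T: 7 to 10 h | 7/95 = 7.4% to 10/93 = 10.8% |
| Ends before the Day 11 morning dose | 24 − 3 = 21 h to 24 − 1 = 23 h | 21/95 = 22.1% to 23/93 = 24.7% |
| Day 11 excluded | 00:00 on Day 11 to T on Day 12: 31 to 34 h | 31/95 = 32.6% to 34/93 = 36.6% |

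The first and third rows rest on the assumed dosing hours; the second does not.

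**Is there a rule elsewhere?** Protocol 8.2.1 groups subjects by treatment received and does not assign event onsets. The sentence on the last dose administered in SAP 10.4.1 defines elapsed time to onset. SAP 7 supplies labels but no onset rule. None of these closes a gap.

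**Laboratory checks.** The post-screening laboratory days include "Days 2, 7, 11 (before ranitidine dosing), 13, 18 (before ranitidine dosing), 22 (before omeprazole dosing), and 24". The Day 22 sample precedes the omeprazole dose, so it is inside the omeprazole-alone window. The Day 11 sample precedes the ranitidine dose and is covered unless Day 11 is excluded.

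**The case against.** The strongest reply is that this is a drafting slip with an obvious intent and little effect. The Day 8 and Day 19 joins show the pattern, and SAP 7 names every phase. An event in a gap would still be listed, would be tabulated if severe or serious, and might appear in the summary by day of onset across the multiple-dosing period. A pre-dose event that worsens after LOXO-292 would fall into the next window. No inferential safety analysis is planned (SAP 10.4.7). The table shells, which are not among the documents available, may hold column definitions or a fallback rule.

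Much of this stands and sets the weight of the point. The ranitidine limb is also the weaker one: the ordinary reading includes Day 11, which leaves only the early hours of Day 12, and excluding Day 11 altogether is strained.

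None of it supplies the missing group. The SAP does not say whether the day-of-onset summary is split by treatment. The Day 22 limit is explicit, so applying the likely intent means overriding the text. Even the most generous of the three readings of the Day 11 limit leaves a gap.

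**Conclusion.** The concern holds and is minor. On the SAP wording, about a quarter of the time on omeprazole alone has no treatment group, given the same approximate clock time on Days 22 and 23. For ranitidine alone the best single figure is 7.4% to 10.8%, with Day 11 included and dosing between 07:00 and 10:00; the narrower readings reach 36.6%. The existence of both gaps is certain on the text, but the size of the second is not. The documents cannot show how many events would start in either gap.

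The possible harm is an undercount in the two antacid-alone columns. Neither condition is named in a study objective. The three LOXO-292 conditions in the secondary objective are essentially unaffected, and the pharmacokinetic analysis is untouched.

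**What to change.** Rewrite the last four windows in SAP 10.4.1 so that each ends where the next begins:

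- Ranitidine alone: from the first ranitidine dose on Day 8 until immediately before the Day 12 LOXO-292 dose.
- LOXO-292 with ranitidine: from the Day 12 LOXO-292 dose until immediately before the Day 19 omeprazole dose.
- Omeprazole alone: from the Day 19 omeprazole dose until immediately before the Day 23 LOXO-292 dose.
- LOXO-292 with omeprazole: from the Day 23 LOXO-292 dose until follow-up.

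Both gaps become 0 h. Starting each window at the dose also covers an event at the moment of dosing, which at present only the Day 1 window does. The table shells should be checked against the new wording.

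The cost is a few sentences before database lock. Only the assignment of TEAEs changes: no dosing, procedure or collected data is affected, and ECG and vital-sign readings stay under SAP 10.1.1, 10.4.4 and 10.4.5.
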